4.1.2 Protocol Deviations

Protocol deviations will be tracked by the study team throughout the conduct of the study. Data will be reviewed prior to unblinding and closure of the database to ensure all important deviations are captured and categorised. Subjects with important protocol deviations liable to influence the efficacy outcomes will be excluded from the PP population. Subjects may also be

identified as having important protocol deviations not leading to exclusion from the PP population.

Important deviations of the protocol procedures may include, but will not necessarily be limited to:

- Violation of inclusion or exclusion criteria at screening
- Non-compliance with study product use
- Use of prohibited treatment or medication before or during the study
- Violation of visit windows

The specific details of important protocol deviations and how these will be assessed will be specified in the Blind Data Review Plan and subjects with important protocol deviations will be identified at the BDRM.

The number and percentage of subjects with at least one important protocol deviation, important protocol deviations not leading to exclusion from PP population with reasons for deviations and subjects with important protocol deviations leading to exclusion from the PP population with reasons for deviations will be summarised by study product group ([Table 14.1.2](#)) and listed ([Listing 16.2.2.1](#)).

All protocol deviations captured on the case report form will be listed in [Listing 16.2.2.2](#). The listing will present date of deviation, deviation type and deviation description.

4.1.3 Analysis Populations

The analysis populations defined for this study are as follows:

Population	Definition / Criteria	Analyses Evaluated
Safety	All randomized subjects who receive at least one dose of study product. This population will be based on the product the subject actually received.	Safety
Modified Intent-To-Treat (MITT) (Treated or exposed)	All randomized subjects who receive at least one dose of study product and have at least one post randomization measure of gum comfort recorded via the questionnaire. This population will be based on the study product to which the subject was randomized. Any subject who receives a randomization number will be considered to have been randomized.	Efficacy
Per Protocol (PP)	All subjects in MITT population who comply with all study procedures and restrictions that may affect the interpretation of the primary response. Deviations will be determined and applied prior to unblinding and consist of variations in criteria likely to affect the interpretation of the efficacy parameters.	Efficacy

NOTES :

Please refer to Attachment 1: List of Data Displays which details the population to be used for each displays being generated.

Subjects excluded from any of the analysis populations will be listed in [Listing 16.2.3.1](#).

The primary population for assessment of efficacy will be the MITT Population. PP population analysis will be performed only if 10% of MITT population is excluded from PP population.

4.2 Subject Demographics and Other Baseline Characteristics

4.2.1 Demographic Characteristics

Descriptive statistics (n, mean, SD, median, minimum and maximum for continuous variables, frequency count [n] and percentage [%] of subjects for categorical variables) will be presented for demographic variables by study product and overall. These variables include age, gender, race and ethnicity and will be presented for the Safety population ([Table 14.1.3.1](#)), the MITT population ([Table 14.1.3.2](#)) and the PP Population ([Table 14.1.3.3](#)) if applicable.

Demographic information will be listed ([Listing 16.2.4.1](#)) for all randomized subjects.

4.2.2 General Medical History

Medical history data will be listed ([Listing 16.2.4.2](#)) with start date and end date or ongoing at the start of the study.

4.2.3 Characteristics of Study Population

[Table 14.1.4.1](#) summarises the baseline characteristic data collected on the denture information (descriptive statistics of duration of denture use), denture history (descriptive statistics of current age of denture), criteria for well-made denture (frequency counts and percentages of all responses to each question), evaluation of well fit denture (frequency counts and percentages of each response under retention and stability and descriptive statistics for sum score retention and stability) and denture bearing tissue evaluation (frequency counts and percentages of responses to ridge shape, tissue resiliency and boarder tissue attachment) eCRF pages for the subjects in the Safety population.

The baseline characteristic table described above will be repeated for the MITT population ([Table 14.1.4.2](#)).

Denture information and history details ([Listing 16.2.4.3](#)), criteria for well-made denture ([Listing 16.2.4.4](#)), evaluation of well-fit denture ([Listing 16.2.4.5](#)) and denture bearing tissue evaluation information ([Listing 16.2.4.6](#)) will be listed as collected on the respective eCRF pages.

4.3 Treatments (Study Product, Rescue Medication, other Concomitant Therapies, Compliance)

Randomization details will be listed, including the planned study product, the actual study product the subject was randomized to and the randomization date ([Listing 16.1.7](#)).

4.3.1 Product Compliance

Product compliance of the experimental adhesive group will be recorded as number of missed product uses since last visit and number of additional product uses since last visit.

Compliance to experimental adhesive use will also be calculated as a percentage at each visit:

$$\text{Compliance} = (\text{actual number of uses} / \text{expected number of uses}) \times 100$$

Where:

Expected number of product uses = number of days between the two visits

Actual number of uses = expected number – missed product uses + additional product uses

The number of missed product uses, additional product uses and percentage compliance will be summarized using descriptive statistics (n, missing, mean, SD, median, minimum and maximum) at Weeks 1, 4, 8 and 12. In addition at Week 12, the number and percentage of subjects <80%, between 80% - 120% and >120% compliance will be presented. Compliance

data will be summarised and listed for the experimental adhesive group only in [Table 14.2.1.1](#) (Safety population) [Table 14.2.1.2](#) (MITT population) and [Listing 16.2.5.1](#).

4.3.2 Prior and Concomitant Medication

Prior or concomitant medication taken by or administered to a subject will be recorded in the case report form. The prior and concomitant medications will be coded using an internal validated medication dictionary, GSK Drug.

Prior medication will be listed by subject, with drug name, GSK drug synonym, dose, dose form, frequency, route, start date, study day relative to randomization date/first use of study product administration and end date ([Listing 16.2.5.2](#)). Prior medications are defined as those which stopped before the date of randomization/first use of the study product. If the stop date is unknown or incomplete and the medication cannot be considered as stopped prior to the randomization date/first use of study product then the medication will be considered as a concomitant medication.

Concomitant medications and significant non-drug therapy will be listed similarly ([Listing 16.2.5.3](#)) with either ongoing or end date displayed. Concomitant medications are defined as medications that are ongoing or started on or after the randomization date/first use of the study product.

For the assignment of prior and concomitant medications, the randomization date will be used for subjects randomized to the No Adhesive group and the date of first use of study product will be used for the subjects randomized to the Experimental Adhesive Group.

Unknown dates will not be imputed, however if the start or stop date is unknown, then it will be assumed to be concomitant medication unless the partial start date or stop date indicates differently.

4.4 Analysis of Efficacy

4.4.1 Primary Efficacy Endpoint

4.4.2 Primary Efficacy Endpoint Definition

The primary endpoint is the change from baseline in the mean overall gum comfort questionnaire score after 12 weeks of study.

The gum-comfort questionnaire is comprised of 5 questions that record the subject-perceived comfort of their denture-bearing tissues. The questions have 5 possible responses (Agree Strongly, Agree Somewhat, Neither Agree or Disagree, Disagree Somewhat, Disagree Strongly) and are scored on a 0 (Agree Strongly) to 4 (Disagree Strongly) scale for all questions. The score from all 5 questions will be summed as the overall gum comfort score at each time point, which will have a range score of 0-20 where a low score is more favorable. See section 4.4.4.1 on how to deal with missing scores.

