## **12 STATISTICAL CONSIDERATIONS AND DATA ANALYSES**

### **12.1 Sample Size Determination**

The primary response variable is the change from baseline in the average of the 5 questions in the Gum Comfort Questionnaire at 12 weeks. There are no comparable data available for the consideration of the analysis of the responses to the Gum Comfort Questionnaire. However, (i) similar questionnaires have been used and reported and (ii) the nature of the response variables using changes from baseline on a 5-point questionnaire allow us to predict the likely distributional aspects of such responses. From this exercise we can assume the standard deviation (SD) of the overall mean of gum comfort response can be represented by a Normal (0.8, 0.0862) random variable.

For a large number of simulated studies 100,000 the SD was sampled from this normal (prior) distribution. A clinically meaningful treatment effect was defined as -0.5 with adhesive vs no adhesive and was introduced into the simulated studies. With 57 evaluable subjects the power to detect such a difference with statistical significance (2-sided) at the 5% level was found to be 90%. This represents the average power to detect a mean difference of -0.5 between treatments over a plausible range (prior distribution) for the unknown SD and is often termed assurance.

In order to account for subject drop outs (assumed as 10%), 63 subjects per treatment arm should be randomized to ensure 57 subjects per arm are evaluable. The MITT population will be used for the primary analysis, and no correction to the alpha testing level will be made in respect of secondary endpoints.

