1.2 Study Objectives

The study objectives are as follows:

Objectives	Endpoints
Primary Objective	Primary Endpoint
To compare the ability of an experimental denture adhesive to provide self-perceived mucosal benefits compared to the use of no adhesive after 12 weeks of product use.	Change from baseline in mean scores of subject responses to the Gum Comfort questionnaire after 12 weeks (overall mean score).
Secondary Objectives	Secondary Endpoints
To compare the ability of an experimental denture adhesive to provide self-perceived mucosal benefits compared to the use of no adhesive after 1, 4 and 8 weeks of product use.	Change from baseline in mean scores of subject responses to the Gum Comfort questionnaire after 1, 4 and 8 weeks (overall mean score).
To compare the ability of an experimental denture adhesive to provide self-perceived mucosal benefits compared to the use of no adhesive after 1, 4, 8 and 12 weeks of product use.	Change from baseline in mean scores of subject responses to the individual questions on the Gum Comfort questionnaire after 1, 4, 8 and 12 weeks.
To compare the ability of an experimental denture adhesive to reduce denture-bearing mucosal irritation compared to the use of no adhesive after 1, 4, 8 and 12 weeks of product use.	Change from baseline in examiner derived scores from the mucosal assessment after 1, 4, 8 and 12 weeks.
To compare the ability of an experimental denture adhesive to provide self-perceived oral health related quality-of-life benefits compared to the use of no adhesive after 1, 4, 8 and 12 weeks of product use.	Change from baseline in mean scores of subject responses to the OHIP-Edent and GOHAI questionnaires after 1, 4, 8 and 12 weeks (overall mean scores and average domain scores).
To assess the sensory attributes of an experimental denture adhesive.	Mean scores of subject responses to the sensory questionnaire after 28 days.
Safety	Safety Endpoints
To assess the tolerability of an experimental denture adhesive.	Treatment emergent adverse events.

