1.4 Sample Size Calculation

The primary response variable is the change from baseline in the average of the 5 questions in The Gum Comfort Questionnaire at 12 weeks. There are no comparable data available for the consideration of the analysis of the responses to the Gum Comfort Questionnaire. However, similar questionnaires have been used and reported and the nature of the response variables using changes from baseline on a 5-point questionnaire allow us to predict the likely distributional aspects of such responses. From this exercise we can assume the standard deviation (SD) of the overall mean of gum comfort response can be represented by a Normal (0.8, 0.0862) random variable.

For a large number of simulated studies 100,000 the SD was sampled from this normal (prior) distribution. A clinically meaningful treatment effect was defined as -0.5 with adhesive vs no adhesive and was introduced into the simulated studies. With 57 evaluable subjects the power to detect such a difference with statistical significance (2-sided) at the 5% level was found to be 90%. This represents the average power to detect a mean difference of -0.5 between treatments over a plausible range (prior distribution) for the unknown SD and is often termed assurance.

In order to account for subject drop outs (assumed as 10%), 63 subjects per treatment arm should be randomized to ensure 57 subjects per arm are evaluable. The Modified Intent-to-Treat (MITT) population will be used for the primary analysis, and no correction to the alpha testing level will be made in respect of secondary endpoints.

2 Planned Analyses

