4.5.1 Efficacy (Secondary)

4.5.1.1 Overall Gum Comfort Score at Weeks 1, 4 and 8

Change from baseline in overall gum comfort questionnaire scores at Weeks 1, 4 and 8 (overall mean score) will be evaluated using the same model as used for primary efficacy analysis on the MITT population (Table 14.2.2.1).

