4.5.1.2 Gum Comfort Questionnaire Individual Questions Scores

Summary of Individual Gum Comfort question scores will be presented (n, missing, mean, SD, SE, median, minimum and maximum) at Weeks 1, 4, 8 and 12 in Table 14.2.3.1. Individual Gum Comfort question scores will be statistical analyzed using the same model as used for primary efficacy analyses in Table 14.2.3.2.

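### Does it matter that the trial is sized on the average of the five Gum Comfort items but analysed on their 0–20 sum?

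*SAP*

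**What the plan says.** The two descriptions of the primary variable sit in different parts of the SAP.

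- **Sizing (SAP 1.4, repeating Protocol 12.1).** "The primary response variable is the change from baseline in the average of the 5 questions". The SD of that quantity "can be represented by a Normal (0.8, 0.0862) random variable". Protocol 12.1 adds: "A clinically meaningful treatment effect was defined as -0.5 with adhesive vs no adhesive".
- **Analysis (SAP 4.4.2).** "The score from all 5 questions will be summed as the overall gum comfort score at each time point", with a range of 0 to 20. SAP 4.4.2.1 tabulates the score over 0 to 20 and uses it in the ANCOVA as both outcome and baseline covariate. The missing-item example in SAP 4.4.3.1 gives 11.25, which is a sum. Protocol 9.2.1.1 also describes a 0–20 total.

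The endpoint wording uses the word mean alongside both. SAP 1.2 has "Change from baseline in mean scores of subject responses to the Gum Comfort questionnaire after 12 weeks (overall mean score"), SAP 4.4.2 has "The primary endpoint is the change from baseline in the mean overall gum comfort questionnaire score after 12 weeks of study", and SAP 4.5.1.1 has "Change from baseline in overall gum comfort questionnaire scores at Weeks 1, 4 and 8 (overall mean score"). Table 5-1, which lists departures from the protocol's analysis, does not mention the scale.

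**The concern.** The primary endpoint appears to have two definitions that differ by a factor of five. If the -0.5 and the SD of 0.8 did not belong to the variable being analysed, the sample size would not support the primary test. Even if the sizing is sound, -0.5 is the only effect the documents call clinically meaningful, and it is printed on a scale other than that of the main result.

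The item-level results add to the risk of confusion. SAP 4.5.1.2 says: "Individual Gum Comfort question scores will be statistical analyzed using the same model as used for primary efficacy analyses". Those tables will be on 0 to 4, the scale of the -0.5, while the overall result will be on 0 to 20. Protocol 2.1 says the study is meant to test product claims and inform practitioners, so the size of the effect will be read as well as its p-value.

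**Working it through.** **Inputs.** From SAP 1.4: 57 evaluable per arm, two-sided 5%, effect 0.5, SD drawn from Normal(0.8, 0.0862), stated power 90%. From SAP 4.4.2: five items scored 0 to 4, summed. From SAP 4.4.3.1: pro-rated score = s·n/(n − m).

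**1. Reproduce the stated power on the average.** For a two-sample t-test with 112 degrees of freedom, the noncentrality is δ / (SD·√(2/57)), and √(2/57) = 0.1873. At SD 0.8 it is 0.5 / (0.8 × 0.1873) = 3.34, and the power is 91.1%. Averaged over 100,000 draws of the SD, with 0.0862 read as a standard deviation, it is 90.4%, which matches the stated 90%. Reading 0.0862 as a variance gives about 86%, which does not match.

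**2. Repeat on the sum.** Multiply everything by 5: δ = 2.5, SD centred on 4.0, spread 5 × 0.0862 = 0.431. The noncentrality is 2.5 / (4.0 × 0.1873) = 3.34 again, and the average power is again 90.4%. As a cross-check, -0.5 set directly against the sum (SD 4.0) would give about 10% power. The -0.5 therefore belongs to the average, and the sizing is coherent once that is recognised.

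**3. The primary test.** Write S = 5A for the score and for its baseline. The model is

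ΔS = a + b·group + c·S₀ + e.

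Dividing by 5 gives

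ΔA = a/5 + (b/5)·group + c·A₀ + e/5.

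The estimate and its standard error both shrink by 5, so their ratio is unchanged. In one simulated data set with 57 per arm:

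| Scale | Difference | SE | p |
|---|---|---|---|
| Sum | -2.273 | 0.805 | 0.0056 |
| Average | -0.455 | 0.161 | 0.0056 |

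The Mann-Whitney fallback uses ranks, which a factor of 5 does not alter. A data transformation, if one were needed, would be applied to the score that section 4 defines, and that is the sum only.

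**4. Missing items.** In the SAP's example the four answers total 9. Pro-rated sum: 9 × 5/4 = 11.25. Average of the answered items: 9/4 = 2.25 = 11.25/5. The factor of 5 survives pro-rating.

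**5. Size of the possible misreading.** The smallest significant difference is t(0.975, 112) × SD × √(2/57). On the sum at SD 4.0 this is about 1.48 (1.17 to 1.80 over the central 95% of the SD prior). That is 59% (47 to 72%) of the converted benchmark of 2.5, but 3.0 (2.3 to 3.6) times an unconverted 0.5. This takes no further gain from the baseline covariate.

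**6. The word mean.** SAP 1.2 also uses overall mean scores for OHIP-Edent and GOHAI, whose overall scores are totals of 0–76 and 0–60. In these documents the phrase can therefore describe the group mean of a total, and SAP 4.4.2.1 frames the primary comparison in that way. Only the word average in SAP 1.4 and Protocol 12.1 conflicts with the sum.

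**The case for a change.** The strongest case for a change is that an average of five questions cannot be read as a group mean of totals, so the conflict is not just loose language. It concerns the primary endpoint. By step 5, a reader who missed the scale would take almost any significant result as exceeding the meaningful effect, including results that reach little more than half of it. One sentence before unblinding would prevent that at almost no cost.

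The textual conflict stands, and so does the factor of five. The consequence is weaker. No section of either document plans to compare the estimate with -0.5, so the figures in step 5 measure a possible reader's mistake and not a property of the analysis; how often it would happen is unknown. The estimate is correct on its own scale, and the SAP states that scale as 0 to 20 where the score is defined. The list of data displays is not reproduced, so the table shells may already carry a scale label. Rewording the endpoint text in SAP 1.2 would also make it differ from Protocol Table 3-1, which it repeats.

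**Conclusion.** This is a clerical inconsistency, and correcting it would gain nothing for the analysis. SAP 1.2 and 1.4 stand under a heading that summarises the protocol; the operative instructions in SAP 4.4.2 to 4.4.3.1 all use the 0–20 sum and leave a programmer one reading. Average power is 90.4% on either scale, the p-value is identical, the sample size stands, and the success rule depends on significance and direction alone.

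The conclusion rests on reading 0.0862 as a standard deviation, which the stated 90% supports, and on the exact factor of 5, which holds with complete items and under the SAP's pro-rating. Anyone who later discusses the size of the effect should set a 0–20 difference against -2.5, or divide it by 5 and set it against -0.5. That is ordinary care in reporting and needs no change to the plan.

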4.4.2.1 Statistical Hypothesis, Model, and Method of Analysis

Descriptive statistics (n, missing, mean, SD, SE, median, minimum and maximum) of the primary variable observed value will be provided ([Table 14.2.2.1](#)) at Baseline, Weeks 1, 4, 8 and 12, along with the change from baseline statistics at Weeks 1, 4, 8 and 12 by product group for the MITT population and ([Table 14.2.2.4](#)) for PP population.

Frequency distributions of the overall gum comfort score by product group will be provided displaying the complete range of responses from 0 – 20 at each week ([Table 14.2.2.2](#)) for MITT population.

The primary analysis is a comparison of the mean change from baseline in overall gum comfort score between Experimental Adhesive and No Adhesive at Week 12 for subjects eligible for the MITT population.

The null hypothesis for the primary endpoint is that the mean change from baseline in overall gum comfort score is equal between the 2 groups.

$$H_0: \mu_1 = \mu_2$$

The alternative hypothesis is that the mean change from baseline in overall gum comfort score is not equal between the 2 groups.

$$H_1: \mu_1 \neq \mu_2$$

The change from baseline in overall gum comfort score at Week 12 will be analysed using analysis of covariance (ANCOVA) with study product as a fixed effect and baseline overall gum comfort score as a covariate. Adjusted means and their SEs, 95% confidence intervals (CI), within treatment p-values for each product group will be displayed with product group difference, SE, 95% confidence interval of the difference and the between-treatment p-value in [Table 14.2.2.3](#) for MITT population and in [Table 14.2.2.5](#) for PP population. All statistical tests of hypotheses will be two-sided and will employ a level of significance of $\alpha = 0.05$.

This study will be considered successful if a statistically significant difference between the adjusted mean scores of the two product groups is observed to be in favor of the Experimental Adhesive.

The assumptions of the ANCOVA model i.e. normality of residual and equality of variances will be investigated. If the assumptions of the underlying model are violated, data transformations will be investigated and if suitable transformations cannot be found, an appropriate non-parametric test will be performed (e.g. Mann-Whitney U test).

All Gum Comfort Questionnaire responses with the overall and change from baseline scores will be listed ([Listing 16.2.6.1](#)).

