### **12.2.5 Primary Analysis**

The primary endpoint is the change from baseline in the mean overall gum comfort questionnaire after 12 weeks of study. The subjects mean change from baseline for the Gum Comfort Questionnaire will be compared between groups using analysis of covariance (ANCOVA) and test between treatment groups at the 5% level of significance. The model will include the baseline value as covariate. Frequency distributions of the responses by treatment group will be provided to detail the whole range of responses. Within and between group estimates of treatment effects will be provided with 95% confidence intervals (CI's). The direction of the effect is anticipated in the direction of an improved gum comfort OHRQoL in favour of the experimental denture adhesive over the no adhesive group.

In the case of the assumptions underlying the model not being supported, a suitable transformation or non-parametric procedure will be used.

No imputation for missing values will be used.

The MITT population will be considered primary for this analysis. Analysis of the PP population (if applicable) will be secondary.

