3.1 Baseline Definition

For all endpoints the baseline value will be the corresponding pre-treatment assessment at Screening/Baseline (Visit 1).

Unless otherwise stated, if baseline data are missing no derivation will be performed and will be set to missing.

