3.4 Timepoints and Visit Windows

The timepoints and visits for this study are defined in the Section 1.1. Any deviation from the study schedule may be reviewed on case-by-case basis at the Blinded Data Review Meeting

(BDRM) to determine whether any data should be excluded from the Per-Protocol (PP) population.

4 Data Analysis

Data analysis will be performed by Syneos Health. The statistical analysis software used will be SAS (Studio) version 9.4 or higher.

Prior to database closure a BDRM will be conducted, during which various aspects of the trial will be discussed and agreed.

Unless otherwise described, all listings will be produced for all randomized subjects.

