4.5.1.4 OHIP-Edent Questionnaire

This questionnaire comprises 19 questions grouped into 6 functional domains as provided in [Table 4-1](#). The questions have 5 possible responses ranging from 0 (Never) to 4 (Very Often) scale for all questions and thus a low score is more favorable and the overall score range is 0-76 where 0 is the best possible score.

Table 4-1 The Functional Domains of the OHIP-Edent Questionnaire

Domain	Questions	Score range
Functional limitations	1-3	0-12
Physical pain	4-7	0-16
Psychological discomfort	8-9	0-8
Physical disability	10-12	0-12
Psychological disability	13-14	0-8
Social disability	15-19	0-20

Summary tables of descriptive statistics (n, missing, mean, SD, SE, median, minimum and maximum) of the observed and change from baseline overall OHIP-Edent score will be presented ([Table 14.2.5.1](#)) at each week and for OHIP-Edent functional domain scores over time ([Table 14.2.5.3](#)) for subjects in the MITT population.

The change from baseline in overall OHIP-Edent score at Weeks 1, 4, 8 and 12 will be analyzed using ANCOVA with study product as a fixed effect and baseline overall OHIP-Edent score as a covariate. Adjusted means and their SEs, 95% CI, within treatment p-values for each product group will be displayed with product group difference, SE, 95% CI of the difference and the between-treatment p-value in ([Table 14.2.5.2](#)). All statistical tests of hypotheses will be two-sided and will employ a level of significance of $\alpha = 0.05$. Similar model will be used to analyze change from baseline OHIP-Edent functional domain scores at weeks 1, 4, 8 and 12 ([Table 14.2.5.4](#)).

As with the primary efficacy analysis, the model assumptions will be checked and suitable transformations or alternative non-parametric method will be performed if these are not met.

All OHIP-Edent responses for each question will be listed ([Listing 16.2.6.3](#)) by functional domain including the functional domain score, change from baseline domain score and overall OHIP-Edent observed and change from baseline values.

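### Within-arm p-values and CIs taken from ANCOVA adjusted means ignore sampling error in the baseline mean, so as tests of zero mean change they exceed the stated 5% (about 6% to 9% if the baseline/Week 12 correlation is 0.7 to 0.2)

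*SAP*

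**What the plan says.** The primary model in SAP 4.4.2.1 is "analysis of covariance (ANCOVA) with study product as a fixed effect and baseline overall gum comfort score as a covariate", fitted to the change at Week 12. From that model the SAP plans to report, by arm and next to the between-arm result: "Adjusted means and their SEs, 95% confidence intervals (CI), within treatment p-values for each product group will be displayed with product group difference". It adds that "All statistical tests of hypotheses will be two-sided and will employ a level of significance" of 0.05.

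SAP 4.5.1.4 (overall OHIP-Edent) and 4.5.1.5 (overall GOHAI) repeat the output at Weeks 1, 4, 8 and 12: "Adjusted means and their SEs, 95% CI, within treatment p-values for each product group". For Gum Comfort at Weeks 1, 4 and 8, the individual Gum Comfort items, and the OHIP-Edent and GOHAI domains, the SAP says only that the same or a similar model will be used.

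The only hypotheses written out in 4.4.2.1 concern equality between the arms. No null is given for the within-treatment tests. The SAP does not say at which baseline value the adjusted means are evaluated or how their SE is computed. On software it says "The statistical analysis software used will be SAS (Studio) version 9.4 or higher" (section 4, Data Analysis) and names no procedure or option. Protocol 12.2.5 requires within-group as well as between-group estimates with 95% CIs.

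**The concern.** A p-value for one arm's adjusted mean change will normally be read as a test that mean change in that arm is zero. The adjusted mean is anchored at the pooled baseline mean of the subjects enrolled, which is itself a sample quantity: "For all endpoints the baseline value will be the corresponding pre-treatment assessment at Screening/Baseline (Visit 1"). With change as the outcome, the baseline slope is negative through regression to the mean. A sample that happens to start high will therefore tend to show a fall in both arms even if nothing has changed. The usual SE does not count that variation.

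The within-arm intervals would then cover less often than 95%, and the within-arm tests would reject more often than the 5% the SAP states. These figures would sit in the main efficacy tables beside a between-arm result that is sound.

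**Working it through.** **Inputs from the documents.** Two-sided alpha 0.05 and ANCOVA of change on product and baseline (SAP 4.4.2.1). 57 evaluable per arm, SD about 0.8 with prior Normal(0.8, 0.0862), difference -0.5 (SAP 1.4).

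**Assumptions.** The baseline/Week 12 correlation ρ is not given, so a range is used. The SDs at baseline and Week 12 are taken as equal (σ) unless stated. Adjusted means are evaluated at the pooled baseline mean with the usual model SE.

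**Step 1: the plan's own figure.** Power = Φ(0.5/(SD·√(2/57)) − 1.96). At SD 0.8 this is Φ(0.5/0.1499 − 1.96) = Φ(1.377) = 91.6%. Averaged over the prior, with 0.0862 read as an SD, it is 90.9% (normal) or 90.5% (t). The stated 90% is reproduced, and 57 is confirmed as a per-arm number.

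**Step 2: the omitted term.** The adjusted mean for arm i is ȳᵢ − b(x̄ᵢ − x̄), where y is change, x is baseline and x̄ is the pooled baseline mean.

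- Usual SE² = s²[1/n + (x̄ᵢ − x̄)²/Sxx], which is conditional on x̄.
- Unconditional variance = that quantity + b²·Var(baseline)/(2n).
- With equal SDs, b = ρ − 1 and the residual variance is σ²(1 − ρ²).
- True/model variance = 1 + (1 − ρ)²/[2(1 − ρ²)] = 1 + (1 − ρ)/[2(1 + ρ)].
- Actual error = 2[1 − Φ(1.96/√ratio)].

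The ratio does not depend on n or on the scale, so summing or averaging the five items makes no difference.

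**Step 3: one case in full.** Take ρ = 0.5 and SD of change 0.8, so σ = 0.8.

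- Model SE = √(0.64·0.75/57) = 0.0918.
- Omitted term = 0.25·0.64/114 = 0.00140.
- Correct SE = √(0.00842 + 0.00140) = 0.0991.
- SE ratio = 1.080; error = 2[1 − Φ(1.96/1.080)] = 7.0%.

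**Step 4: the range.** The simulation used 40,000 trials per setting, 57 per arm and t tests on 111 df.

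| ρ | True/model SE | Error, formula | Error, simulated | CI coverage, formula |
|---|---|---|---|---|
| 0.2 | 1.155 | 9.0% | 8.8% | 91.0% |
| 0.3 | 1.127 | 8.2% | 8.1% | 91.8% |
| 0.5 | 1.080 | 7.0% | 7.0% | 93.0% |
| 0.7 | 1.043 | 6.0% | 5.9% | 94.0% |
| 0.9 | 1.013 | 5.3% | 5.2% | 94.7% |

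**Step 5: sensitivity.**

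- A discrete 0–20 score gave 8.1%, 7.1% and 5.8% at ρ = 0.3, 0.5 and 0.7.
- With the Week 12 SD at 0.8 or 1.2 times the baseline SD and ρ from 0.3 to 0.7, the error ran from 5.2% to 10.8%.
- If 0.8 is the SD of change, then ρ = 1 − 0.64/(2·σ²). An assumed baseline SD of 0.7 to 1.0 gives ρ = 0.35 to 0.68 and an error of 7.9% to 6.1%.

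**Step 6: confirming the cause.** With the omitted term added, the simulated error was 4.7% to 5.0% for every ρ from 0 to 0.9. A paired t-test on raw change gave 4.8% to 5.1%. In the between-arm difference x̄ cancels, and the simulated error there stayed at 4.8% to 5.2%.

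**Step 7: how many results.** Gum Comfort Week 12 (1) + overall OHIP-Edent at four weeks (4) + overall GOHAI at four weeks (4) = 9 MITT analyses. Two arms give 18 within-treatment p-values.

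**The case against.** The best defence is that an adjusted mean is by construction the mean at a given baseline value. If inference is meant only for subjects whose mean baseline equals the one observed, the usual SE is right and 5% holds. This is correct, but the SAP does not state that restriction, and a reader will take the p-value as a statement about mean change in the arm.

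The second defence is that nothing is decided on these values. The stated hypotheses and the success rule in SAP 4.4.2.1 are between-arm, and SAP 4.5 calls the secondary variables non-definitive. This stands and limits the consequence.

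Third, raw change means and SEs by arm are already planned for the three overall scores, so a reader could form the unconditional interval. That is true, but it does not mend the CI and p-value printed from the model.

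Three stronger readings are tempting and not supported:

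- A reader might infer that every ANCOVA in the SAP carries the fault. Within-treatment p-values are explicit only for the nine analyses counted above. They extend to other weeks, items and domains only if the same or a similar model brings the same output, and the list of displays is not shown.
- A reader might infer that the main comparison is affected. It is not, because the term cancels.
- A reader might count a change shared by both arms as a further false positive. Such a change is real, and any valid within-arm test would tend to detect it. Part of the extra sensitivity of the adjusted mean is legitimate ANCOVA precision. That the change may not be due to the product is a matter of interpretation, separate from this SE.

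**Conclusion.** The point holds for the within-arm results only. As tests of zero population mean change, the planned within-treatment p-values are anti-conservative and their CIs too narrow. The true SE is about 4% to 15% larger than the model SE for ρ from 0.7 down to 0.2 with equal SDs, and the inflation is negligible at ρ = 0.9.

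The size rests on a correlation the documents do not give, on the equal-SD assumption, and on the usual conditional SE being used. The SAP does not state that SE in words, but it names no other. The 6% to 9% range is therefore conditional and is not a property fixed by the plan. The direction does not depend on the exact correlation: unless the slope of change on baseline is zero, the omitted term is positive.

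**What to change.** In SAP 4.4.2.1, 4.5.1.4 and 4.5.1.5, drop the within-treatment p-values from Tables 14.2.2.3, 14.2.5.2 and 14.2.6.2, and from 14.2.2.5 if the per-protocol analysis is run. State whether the other tables based on the same or a similar model show any within-arm inference, and treat them alike.

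Keep a within-arm 95% CI, since protocol 12.2.5 requires it, and take it from one of two sources:

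- the raw paired change, whose mean and SE are already planned in Tables 14.2.2.1, 14.2.5.1 and 14.2.6.1; or
- the adjusted mean, with b²·Var(baseline)/N added to its squared SE, where N is the number of subjects in the model.

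If a within-arm p-value is kept, compute it the same way and state its null. Keep the ANCOVA for the between-arm difference.

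The cost is SAP wording and table shells. Within-arm results will look slightly less favourable. The paired option also loses some precision: paired SE/correct adjusted SE = √[4/(3 + ρ)], which is 1.12 at ρ = 0.2, 1.07 at 0.5 and 1.04 at 0.7. Raw arm changes will also not subtract exactly to the adjusted difference shown beside them. The second option avoids both drawbacks but needs a short extra calculation.
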